1.0 Objectives / Specific Aims

The overall objective of this double blind, sham controlled study is to evaluate the feasibility, tolerability, and preliminary efficacy of using a single day accelerated course of repetitive transcranial magnetic stimulation (rTMS) to decrease smoking cue induced nicotine craving in smokers.

- Aim 1: Determine if the delivery of a course of five rTMS sessions during a single day is feasible and well tolerated in participants with nicotine use disorder. We will test the hypothesis that greater than 75% of participants who start the rTMS course will complete the 5 treatments, and greater than 75% of participants will tolerate a treatment dose of greater than 100% rMT.
- Aim 2: Determine if nicotine dependent participants will experience a decrease in cue induced nicotine craving after 5 sessions of rTMS. We hypothesize that participants receiving active rTMS will have a greater decrease in cue induced nicotine craving after a five session treatment course of active rTMS when compared to those participants receiving sham rTMS.

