2.0 Intervention to be studied

Study Intervention: Left dorsolateral pre-frontal cortex (LDLPFC) rTMS stimulation with parameters of each session delivering 3000 pulses of up to110% motor threshold 10hz stimulation, 5 seconds on 10 seconds off. The accelerated course will consist of 5 sessions delivered during a single day for a total of 15,000 pulses.

Control: Sham sessions will be delivered using an electronic sham system consisting of a coil that mimics the appearance and sound of TMS, combined with a transcutaneous electrical nerve stimulation (TENS) device which produces a small electric shock mimicking the feeling of real TMS. This type of sham has been demonstrated to be indistinguishable from active TMS, has been well tolerated in [9, 18], and successfully used in other clinical trials[20, 21].

3.0 Study Endpoints:

Aim 1: Determine if the delivery of a course of five rTMS sessions during a single day is feasible and well tolerated in participants with nicotine use disorder. Primary endpoint will be the percent of participants starting the rTMS treatment who complete all 5 rTMS treatments in a single day.

Aim 2: Determine if nicotine dependent participants will experience a decrease in cue induced nicotine craving after 5 sessions of rTMS. Primary endpoint of difference in 0-100 averaged pre and post treatment smoking cue induced cigarette craving scores using an adopted QSU- B 10 questionnaire to measure smoking craving [12]. A secondary endpoint will be the trend of level of neutral cigarette craving evaluated between each rTMS treatment session. An exploratory endpoint will be comparison of participant self-reported level of smoking the week prior to treatment with smoking 1 and 2 weeks after treatment, assessed by phone call.

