10.0 Study Design / Methods

The study will be a double blind, sham controlled design comparing cue induced nicotine craving before and after five sessions of active or sham rTMS. Participants will be recruited and will undergo a short phone screen to see if they qualify. The study will involve a single visit and participants will be asked to abstain from smoking or using nicotine replacement during the study visit. At the beginning of the visit study personnel will obtain informed consent from participants and confirm participants meet study inclusion criteria through administration of the MINI neuropsychiatric interview[22], review of current medications, medical history, urine pregnancy test if indicated and confirmation of smoking status by exhaled CO reading of >10ppm. The participants smoking history will be taken using the time line follow back and the Fagerstrom Test for Nicotine Dependence (FTND) will be administered to evaluate the severity of nicotine dependence[23]. Participants will be randomized to receive either sham rTMS or active rTMS. Participants cue induced nicotine craving will be evaluated before and the rTMS session. A week and 2 weeks after the participant's rTMS, they will be contacted by telephone and asked their current level of cigarette consumption.

rTMS treatments: rTMS will be delivered via a MagPro double blinded rTMS Research System (MagVenture, Denmark) with a Cool-B65 Butterfly Coil (a combined active and sham coil). We will use a standard resting motor threshold (rMT) determination to determine the TMS dose [24]. Treatment will be delivered at up to 110% resting motor threshold. Each active TMS session will consist of a total of 3000 pulses of 10Hz stimulation (5s-on,10s-off)[12]. Each treatment day will consist of 5 sessions of rTMS, each separated by approximately 30 minutes. A prior accelerated rTMS investigation has separated

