15.0 Risks to Subjects

Potential risks of rTMS: The use of high frequency rTMS has been FDA approved for the treatment of major depressive disorder since 2008. Our stimulation parameters of 3000 pulses of 10Hz stimulation (5s-on,10s-off) are very similar to the FDA approved protocol (3000 pulses, 10Hz, 4-Seconds on, 8-Seconds off), and has been used safely in a prior rTMS study targeting nicotine craving [12]. The common clinical dose of rTMS in depression is 36 treatments with 3000 pulses per treatment, for a total of 108,000 pulses[28]. Prior accelerated rTMS studies in depression have safely delivered 6,000 pulse treatments three times a day, delivering 18,000 daily pulses for a total of 54,000 pulses over three days [18]. We will deliver 5 sessions of 3,000 pulses for a total of 15,000 pulses in a day meaning we will be giving fewer pulses than a typical course of rTMS and fewer daily pulses than a prior accelerated rTMS study safely provided. Accelerated treatment paradigms have been safely delivered in both depression[17, 18, 25, 29], and addictions [19, 30] populations without any clear adverse effect.

Risk of Seizure: The most serious risk associated with the use of rTMS is seizure. Since the adoption and widespread use of standard safety guidelines in 1997 [31], there has only been one documented seizure using a figure of eight coil like we will be using. The risk of seizure has been estimated to be less than 0.1% which is lower than the risk of seizure associated with pharmacologic antidepressants[32]. The risk of seizure is related to the various stimulation parameters (intensity, frequency, train duration), location of application, pre-existing risk of seizure, and substance/medication factors. In the very rare event a seizure is caused, removing the coil is typically sufficient to stop the seizure, and there is no increased risk of subsequent seizures. In order to mitigate the risk of seizure we will carefully individualize the intensity of stimulus (by performing a resting motor threshold determination), treat using standard treatment protocols and exclude potential participants at higher risk of seizure (those with a past history of seizures, those with known CNS lesions, those in withdrawal from alcohol or benzodiazepines, etc).

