Risk of site discomfort and headache: Two relatively common risks associated with the use of rTMS include the risk of mild transient site discomfort during treatment (most patients), and the risk of post treatment headache (Approximately 5%). Both of these potential side effects are typically mild. In terms of mitigating site discomfort, we will slowly ramp up stimulation intensity during the first sessions. In our experience both clinically and experimentally, ramping initial sessions results in improved tolerability of treatment. Additionally, due to the anti-pain effect of rTMS participants rapidly adjust to stimulation. In the unusual circumstance that a headache is caused by rTMS, over the counter analgesics are typically sufficient to alleviate the headaches, and we will forewarn participants of the possibility of headache and the effectiveness of over the counter analgesics.

Potential for hearing loss: The discharge of the TMS coil generates a high-energy click that may cause cochlear damage. Humans exposed to TMS have shown temporary increases in auditory threshold (especially at high frequencies) lasting at least 5 minutes and less than 4 hours. Foam earplugs can protect against these changes and will be worn during TMS sessions.

Safety in the case of pregnancy: This protocol will exclude pregnant women. Pregnancy status will be confirmed during the baseline visit with a urine pregnancy test.

Safety in case of thoughts of harming self: If a patient endorses thoughts of suicide during the visit, the patient will be evaluated by a psychiatrist and appropriate referrals made for emergency treatment if needed or outpatient follow up. If evaluation is performed by a resident psychiatrist, the evaluation will be discussed with an attending psychiatrist.

Potential Risks of Cue Induced craving: Visualization of drug cues are known to transiently increase craving for substances including nicotine. These visual cues will be presented in the presence of study staff under close monitoring so participants will not be able to immediately smoke. Participants will be given referral information to providers to assist in smoking cessation should they wish to quit and additionally VA participants will be informed about the smoking cessation group at the VA.

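### Aim 1 asks whether the course is well tolerated, but Section 3.0 measures only completion of five sessions, and the document provides for no collection or by-arm reporting of the side effects it expects

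*Combined protocol and SAP*

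**What the plan says.** Section 1.0 states Aim 1 as follows: "Determine if the delivery of a course of five rTMS sessions during a single day is feasible and well tolerated". The statistical text in Section 12.0 makes feasibility and tolerability of the accelerated treatment the main objective of the pilot.

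The document sets two Aim 1 criteria but carries only one into the endpoints:

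- **Section 1.0, hypotheses.** More than 75% of starters complete the five treatments, and "greater than 75% of participants will tolerate a treatment dose of greater than 100% rMT".
- **Section 3.0, endpoint.** "Primary endpoint will be the percent of participants starting the rTMS treatment who complete all 5 rTMS treatments in a single day". The dose criterion does not appear.

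Section 15.0 sets out what participants may experience. On the common effects it names "the risk of mild transient site discomfort during treatment (most patients), and the risk of post treatment headache (Approximately 5"%). On hearing: "Humans exposed to TMS have shown temporary increases in auditory threshold". On seizure: "The risk of seizure has been estimated to be less than 0.1"%. For each of these it describes how the risk is reduced or handled, not how occurrences are recorded.

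For follow-up, Section 10.0 says that one and two weeks after treatment participants are telephoned: "they will be contacted by telephone and asked their current level of cigarette consumption". Section 3.0 likewise mentions the calls only for the exploratory smoking endpoint. The planned analyses in Section 12.0 concern change in craving.

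**The concern.** Completion is a coarse measure of tolerability. A participant who has marked scalp discomfort or a headache and stays for the fifth session is a success on the Section 3.0 endpoint, indistinguishable from a participant who felt nothing. Followed as written, the trial could report that the course was well tolerated without any symptom data behind the statement.

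This matters because tolerability is part of the main objective, and because the pilot is meant to inform the planning of later studies. Those studies will need to know how often participants had side effects and how uncomfortable each session was. Symptoms not recorded on the treatment day cannot be recovered reliably afterwards.

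Reporting by arm adds something further. The sham combines a coil that imitates TMS with a device that gives a small electrical stimulus, so sham participants may feel discomfort too. Without records in both arms, discomfort from active stimulation cannot be told apart from discomfort due to the procedure.

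**Working it through.** The plan gives no derivation of its sample size and sets statistical power aside, so there is no figure of its own to reproduce. The check is first a comparison of sections and then arithmetic for scale.

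**1. Sections side by side**

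| Element | Where | Counts side effects? |
|---|---|---|
| Aim 1 question: feasible and well tolerated | 1.0, 3.0 | Not applicable |
| Completion of five sessions | 1.0, 3.0 | No |
| More than 75% tolerate above 100% rMT | 1.0 only | No; records dose reached |
| Calls at 1 and 2 weeks | 3.0, 10.0 | None described; smoking only |
| Statistical analysis | 12.0 | No; craving change only |
| Expected harms | 15.0 | No; mitigation and handling only |

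No section provides an adverse-event form, symptom checklist, discomfort rating or safety table.

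**2. Inputs for scale**

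- n = 15 per arm (Section 6.0).
- Headache rate 5%, seizure rate below 0.1%, and discomfort in most patients (Section 15.0).

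**3. Expected events among 15 active participants**

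- Headache: 15 × 0.05 = 0.75 expected.
- P(at least one) = 1 − 0.95^15 = 0.537.
- P(at least two) = 1 − 0.95^15 − 15 × 0.05 × 0.95^14 = 0.171.
- Discomfort: most patients means more than half, so more than 15 × 0.5 = 7.5.
- Seizure at 0.1%: 15 × 0.001 = 0.015 expected.

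Section 15.0 does not say whether 5% is per participant or per session. The figures above take it per participant. If it were per session and sessions were independent (both assumptions), the per-participant risk would be 1 − 0.95^5 = 0.226, or 15 × 0.226 = 3.4 participants. The range is therefore about 0.75 to 3.4.

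**4. What completion alone could show**

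If all 15 active participants complete, the exact two-sided 95% interval has lower limit 0.025^(1/15) = 0.782, so 78.2% to 100%. That describes completion and says nothing about the frequency of side effects.

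**5. What recorded side effects could show**

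- 0 of 15: upper limit of the exact two-sided 95% interval = 1 − 0.025^(1/15) = 0.218.
- 1 of 15: 6.7%, exact 95% interval 0.2% to 31.9%.

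For a comparison of arms, assume 5% in sham and two-sided alpha 0.05. With p̄ the mean of the two rates, the normal approximation is

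power = Φ{[d − 1.96·√(2p̄(1−p̄)/15)] / √[(p₁(1−p₁) + p₂(1−p₂))/15]}, where d = p₂ − p₁.

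For 5% against 20%: d = 0.15, p̄ = 0.125, and power = Φ[(0.15 − 1.96 × 0.1208)/0.1176] = 0.23. The same formula gives 0.43 for 30%, 0.64 for 40% and 0.82 for 50%. The approximation is rough at these counts, but it is enough to show that only very large differences could be detected.

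**The case against.** The strongest case on the other side has several parts.

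- **There is a second tolerability criterion.** This is true, so it would be wrong to infer that tolerability is judged by completion alone. Intensity goes up to 110% rMT and is ramped in the first sessions to limit discomfort (Sections 10.0 and 15.0), so discomfort can show up as a lower dose without the participant stopping. But the criterion is missing from Section 3.0, and someone who reaches the dose with symptoms still passes.
- **Silence is not proof.** A reader might infer that harms will never be counted. The document does not establish that. Staff may record events under institutional rules, and the section numbers skip 4, 11, 13, 14 and 17. The gaps do not show that a safety section exists, but they rule out a flat denial. Nor does Section 10.0 say that nothing else is asked in the calls. What stands is that no endpoint or analysis shown would use such records.
- **No comparison with sham is promised.** Both Aim 1 hypotheses are thresholds, and the active-versus-sham hypothesis belongs to Aim 2. The lack of a by-arm comparison therefore does not defeat the stated objective. By-arm reporting is advisable for interpretation.
- **The listed harms are mostly same-day.** Discomfort occurs during treatment, and the hearing change is described as lasting less than 4 hours. Headache is the listed effect most plausibly first felt at home, and a call a week later relies on recall. The larger gap is the visit itself, and the calls are secondary.
- **Payment.** A reader might suspect that compensation inflates completion. Section 8.0 pays $120 for eligibility and participation and does not tie it to finishing five sessions, so this is not supported.
- **Small numbers.** Recording events in sham does not narrow the active-arm interval, and a formal comparison has little power. This stands, and it is why the data should be presented descriptively.

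**Conclusion.** The concern holds in a limited form. Tolerability is part of the main objective, but Section 3.0 measures it only by completion, leaves out the plan's own dose criterion, and has no measure of the side effects that Section 15.0 expects. The plan as written can report completion. It has no endpoint describing what participants experienced in completing the course.

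On size, discomfort would be expected in more than half of the active arm and headache in about 0.75 of 15 at the stated 5%, rising to about 3.4 if 5% is per session and independent. None of these events affects the endpoint unless the participant stops. With 15 per arm, recorded data would be descriptive: 0 of 15 is compatible with a true rate of up to about 22%.

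The conclusion assumes that no adverse-event procedure exists outside the document. If one does, collection is not the gap, and what remains is that its results are not named as an Aim 1 endpoint. The craving endpoint and its analysis are unaffected. The change should be made, but its absence does not invalidate the trial.

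**What to change.** 1. **Section 3.0, Aim 1.** Carry over the Section 1.0 criterion on tolerating a dose above 100% rMT, so that endpoints and hypotheses agree.
2. **Section 3.0, Aim 1.** Add the number and percent of participants with any adverse event, and a brief discomfort rating after each of the five sessions. A 0–10 scale is one option among several.
3. **Section 12.0, Statistical Analysis.** State that these are reported descriptively by arm, with exact 95% confidence intervals for proportions and no formal test.
4. **Section 10.0, secondarily.** Add an open adverse-event question to the existing 1- and 2-week calls.

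If an adverse-event form is already in use, the adverse-event part reduces to naming its results as an Aim 1 endpoint.

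The cost is a short REDCap form and about a minute per session and per call. No extra visit, staff, procedure or participants are needed.

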12.0 Data Management

Data will be managed using REDCAP and all data entry will take place directly into REDCAP in a deidentified manner, so that PHI will not be stored in REDCAP. A printed key linking REDCAP participant number with the participant name and contact information will be kept in a locked filing cabinet at the study location (VA participant information will be locked in cabinet at the VA). The only required paper items will be the consent and HIPAA documents. There will however be emergency paper backups of the database should the database be unavailable for any reason. If data is collected on paper, the information will be immediately transferred to the REDCAP database, and the paper record will be kept in a locked filing cabinet.

Statistical Analysis:

In preliminary analyses, we will examine the change in craving from pre-treatment to post-treatment in both groups (active rTMS vs. sham rTMS), and will use an independent two-group t-test to evaluate the difference in magnitude of change between the two groups. In final analyses, we will fit a generalized linear model to examine the impact of active vs. sham treatment on the magnitude of change from pre- to post-treatment craving. We will control for baseline craving since it is expected to be a strong predictor of post-treatment craving and may be imbalanced between study groups.

The main objective of this pilot study is to establish feasibility and tolerability of the accelerated rTMS treatment, and to begin to explore the possible treatment effect. Therefore, we do not focus on statistical power for this project. We aim to recruit 15 patients per group, which will provide a good foundation for estimating likely effect size and planning future studies.

15.0 Risks to Subjects

Potential risks of rTMS: The use of high frequency rTMS has been FDA approved for the treatment of major depressive disorder since 2008. Our stimulation parameters of 3000 pulses of 10Hz stimulation (5s-on,10s-off) are very similar to the FDA approved protocol (3000 pulses, 10Hz, 4-Seconds on, 8-Seconds off), and has been used safely in a prior rTMS study targeting nicotine craving [12]. The common clinical dose of rTMS in depression is 36 treatments with 3000 pulses per treatment, for a total of 108,000 pulses[28]. Prior accelerated rTMS studies in depression have safely delivered 6,000 pulse treatments three times a day, delivering 18,000 daily pulses for a total of 54,000 pulses over three days [18]. We will deliver 5 sessions of 3,000 pulses for a total of 15,000 pulses in a day meaning we will be giving fewer pulses than a typical course of rTMS and fewer daily pulses than a prior accelerated rTMS study safely provided. Accelerated treatment paradigms have been safely delivered in both depression[17, 18, 25, 29], and addictions [19, 30] populations without any clear adverse effect.

Risk of Seizure: The most serious risk associated with the use of rTMS is seizure. Since the adoption and widespread use of standard safety guidelines in 1997 [31], there has only been one documented seizure using a figure of eight coil like we will be using. The risk of seizure has been estimated to be less than 0.1% which is lower than the risk of seizure associated with pharmacologic antidepressants[32]. The risk of seizure is related to the various stimulation parameters (intensity, frequency, train duration), location of application, pre-existing risk of seizure, and substance/medication factors. In the very rare event a seizure is caused, removing the coil is typically sufficient to stop the seizure, and there is no increased risk of subsequent seizures. In order to mitigate the risk of seizure we will carefully individualize the intensity of stimulus (by performing a resting motor threshold determination), treat using standard treatment protocols and exclude potential participants at higher risk of seizure (those with a past history of seizures, those with known CNS lesions, those in withdrawal from alcohol or benzodiazepines, etc).

Risk of site discomfort and headache: Two relatively common risks associated with the use of rTMS include the risk of mild transient site discomfort during treatment (most patients), and the risk of post treatment headache (Approximately 5%). Both of these potential side effects are typically mild. In terms of mitigating site discomfort, we will slowly ramp up stimulation intensity during the first sessions. In our experience both clinically and experimentally, ramping initial sessions results in improved tolerability of treatment. Additionally, due to the anti-pain effect of rTMS participants rapidly adjust to stimulation. In the unusual circumstance that a headache is caused by rTMS, over the counter analgesics are typically sufficient to alleviate the headaches, and we will forewarn participants of the possibility of headache and the effectiveness of over the counter analgesics.

Potential for hearing loss: The discharge of the TMS coil generates a high-energy click that may cause cochlear damage. Humans exposed to TMS have shown temporary increases in auditory threshold (especially at high frequencies) lasting at least 5 minutes and less than 4 hours. Foam earplugs can protect against these changes and will be worn during TMS sessions.

Safety in the case of pregnancy: This protocol will exclude pregnant women. Pregnancy status will be confirmed during the baseline visit with a urine pregnancy test.

Safety in case of thoughts of harming self: If a patient endorses thoughts of suicide during the visit, the patient will be evaluated by a psychiatrist and appropriate referrals made for emergency treatment if needed or outpatient follow up. If evaluation is performed by a resident psychiatrist, the evaluation will be discussed with an attending psychiatrist.

Potential Risks of Cue Induced craving: Visualization of drug cues are known to transiently increase craving for substances including nicotine. These visual cues will be presented in the presence of study staff under close monitoring so participants will not be able to immediately smoke. Participants will be given referral information to providers to assist in smoking cessation should they wish to quit and additionally VA participants will be informed about the smoking cessation group at the VA.

Potential Loss of Confidentiality: There is risk that a participant may lose confidentiality due to collection and storage of protected health information. To minimize this risk, patient data stored in REDCAP will be deidentified using a participant ID number. The key linking this participant ID number to their name and contact information will be stored in a locked filing cabinet at each study location. VA PHI will be locked up at the VA and not leave its premises, nor be accessed by non-VA study personnel. The is also the potential that study personnel may have a legal obligation to break confidentially in the rare case of learning information such as the patient is an imminent risk to themselves/others or learning of potential child/elder abuse.

